As the Principal Investigator, I will assure that no deviation from, or changes to the protocol will take place knowingly without prior agreement from the sponsor and documented approval from the Institutional Review Board (IRB), or other approved Ethics Committee, except where necessary to eliminate an immediate hazard(s) to the trial participants.

All key personnel (all individuals responsible for the design and conduct of this trial) have completed Human Participants Protection Training and GCP Training. Further, I agree to ensure that all staff members involved in the conduct of this study are informed about their obligations in meeting the above commitments.

Investigator's Name:

Site Name/Number:

[figure not shown]
PROTOCOL SUMMARY

Title	Diabetes Endothelial Keratoplasty Study: Impact of Diabetes on Corneal Transplant Success and Endothelial Cell Loss (DEKS)
Précis	The association of diabetes in the cornea donor with transplant success and loss of endothelial cells one year following Descemet membrane endothelial keratoplasty (DMEK) will be evaluated in a double-masked multi-center trial in which study eyes will be assigned to receive either a cornea from a donor without diabetes or a cornea from a donor with diabetes.
Objectives	
 • To determine if the 1-year graft success rate following DMEK performed with corneas from donors without diabetes is superior to the graft success rate with cornea donors with diabetes. • To determine if the 1-year central endothelial cell loss (ECL) following DMEK performed with corneas from donors without diabetes is superior to the central ECL when corneas from donors with diabetes are used. • To explore the relationship of severity of diabetes in the donor, as measured by eye bank-determined diabetes risk categorization scores, post-mortem hemoglobin A1c (HbA1c), and skin advanced glycation endproducts (AGE) and oxidation markers, with 1-year graft outcomes (i.e., graft success and ECL) following DMEK in corneas from donors with diabetes.
Study Design	Prospective, randomized, double-masked (participant and clinical site) clinical trial
Number of Sites	~30 clinical sites and ~16 eye banks in the United States

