Endpoint	
Primary Efficacy Outcome: Graft failure within 1 year of surgery
 
Key Secondary Efficacy Outcomes: Change in central endothelial cell density (ECD) at 1 year after surgery
 
Key Safety Outcomes: Endophthalmitis, microbial keratitis (bacterial, fungal, parasitic) within 3 months of DMEK, and other unexpected ocular serious adverse events (SAEs).
 
Other Key Analyses: Develop separate models for predicting 1) risk of graft failure and 2) ECL based on severity of diabetes in the donor as measured by eye bank-determined diabetes risk categorization scores, post-mortem HbA1c, and skin advanced glycation endproducts (AGE) and oxidation markers.

Population	
Participant Inclusion Criteria:
 
 1) Age range 30- < 91 years with minimum life expectancy of at least 1 year 2) Willingness to return to study site for follow up at 1 month and 1 year 3) Fluent in English or Spanish 4) Willingness to have fingerstick blood sample collected to determine HbA1c level at entry and at 1 year. The participant must agree to have their primary care provider contacted (or an appropriate referral provided) if they were not known to have diabetes and the HbA1c suggests they may have diabetes. Similarly, if already known to have diabetes and the HbA1c is high, the participant must agree to have their primary care provider contacted or an appropriate referral provided. 
Study Eye Eligibility Criteria
 
Inclusion:
 
 1. At least one eye clinically recommended for DMEK that is able to be scheduled for DMEK between 5 to 90 days after enrollment 2. If second eye is enrolled, must be scheduled for DMEK between 7 days and 6 months after DMEK on the first eye. 3. Presence of a condition related to endothelial dysfunction which will be treated by DMEK 
 • Eligible indications for DMEK include: 
 a. Presence of Fuchs endothelial corneal dystrophy (FECD) meeting at least one of the following:

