8.4.2 Secondary Endpoint

Endothelial cell density at 1 year is considered a secondary endpoint.

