8.7 Analysis of the Secondary Endpoint

For ECD, only participants with a gradable 1-year image who have not experienced graft failure 1-year after DMEK will be included in the analysis. There will be no imputation of missing data. Summary statistics (mean \pm SD or median (IQR)) appropriate to the distribution will be tabulated by donor diabetes status group and at baseline, 1-year and for the changes from baseline to 1-year.

Repeated measures regression models with unstructured covariance including data from baseline, 1 month, and 1 year will be used to compare donor diabetes status effects while adjusting for baseline ECD, corneal diagnosis, and recipient study eyes (random effect. A point estimate, 95% confidence interval, and two-sided p-value will be reported for the donor diabetes status effect based on the linear regression model. Residual values will be examined for an approximate normal distribution. If residual values from the regression model have a skewed distribution then an appropriate transformation, truncation, or a nonparametric analysis based on ranks will be performed. Descriptive analyses (e.g., boxplots) stratified by donor diabetes status group will be given at baseline, 1 month, and 1 year.

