8.12 Sub-Group Analyses

Subgroup analyses/assessments of effect modification (interaction) will be conducted separately for the graft failure within the first year after surgery and ECD at one-year. These analyses will be considered exploratory. Additionally, interpretation of the analyses will depend on whether the overall analysis demonstrates a significant treatment group difference; in the absence of such an overall difference, subgroup analyses will be interpreted with caution. The general approach for these exploratory analyses will be to add an interaction term for the subgroup factor, which will be noted in the SAP, by diabetes group into the models used for the primary analyses. For

continuous variables, results will be displayed in subgroups based on cutpoints although the analysis will utilize the variable as continuous. If there is insufficient sample size in a given subgroup, the cutpoints for continuous measures may be adjusted per the observed distribution of values. Cutpoint selection for display purposes will be made masked to the outcome data.

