8.14 Analysis of the Tertiary Exploratory Endpoint

Exploratory analyses will evaluate the effect of donor diabetes status on 1-year graft failure rate with donor diabetes severity defined in the alternative ways as measured by eye bank-determined diabetes risk categorization scores, post-mortem HbA1c, and skin AGEs and oxidation markers. Additionally, the effect of donor diabetes status on 1-year ECD with alternative definitions for donor diabetes severity will be examined. The alternative definitions will be detailed in the SAP.

Potential confounders or interaction terms determined in the analyses of graft failure and ECD will be explored in adjusted models mirroring the primary analyses.

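### The secondary ECD model uses baseline ECD as both repeated outcome and covariate, and does not name the 1-year donor contrast that the endpoint calls for

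*Combined protocol and SAP*

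**What the plan says.** The 1-year target is consistent across the protocol:

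- Protocol Summary, Objectives: "To determine if the 1-year central endothelial cell loss (ECL) following DMEK performed with corneas from donors without diabetes is superior".
- Protocol Summary, Endpoint: "Change in central endothelial cell density (ECD) at 1 year after surgery".
- Section 8.4.2: "Endothelial cell density at 1 year is considered a secondary endpoint".
- Section 8.12: subgroup analyses "will be conducted separately for the graft failure within the first year after surgery and ECD at one-year".

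Section 8.7 gives the model. It is a repeated measures regression whose covariance is unstructured, described as "including data from baseline, 1 month, and 1 year will be used to compare donor diabetes status effects while adjusting for baseline ECD", with corneal diagnosis and a random effect for recipient study eyes as the other terms. The reported result is a point estimate and 95% confidence interval, and a "two-sided p-value will be reported for the donor diabetes status effect based on the linear regression model". No time point is attached to that effect. The analysis set is eyes with a gradable 1-year image and no graft failure.

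Two other sections build on these models. Section 8.12 adds an interaction of the subgroup factor "by diabetes group into the models used for the primary analyses". Section 8.14 says that confounders and interactions "will be explored in adjusted models mirroring the primary analyses".

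**The concern.** There are two separate gaps.

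1. **Role of baseline.** Data that enter a repeated measures model under an unstructured covariance are outcome data. Baseline ECD therefore appears on both sides of the equation. The analyst must drop one of the two roles, and the text does not say which. The choice matters because donor diabetes and baseline ECD are both properties of the donor tissue.

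2. **Which effect is reported.** A repeated measures model with a single donor term does not estimate the 1-year difference unless the donor effect is the same at every visit in the model. Section 8.7 neither names a donor-by-visit term nor says which visit the reported effect belongs to.

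This is the analysis of the trial's second objective. A common effect would be too small if the donor effect grows after 1 month and too large if it shrinks. The ECD subgroup and severity analyses would inherit whichever form is chosen.

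**Working it through.** The documents state no ECD figure that could be reproduced, so the check has two parts.

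**Part 1: the model as written.** In the baseline row the equation is Y0 = a + b·Y0 + d·D + e, where D is donor diabetes status. Setting a = 0, b = 1 and d = 0 makes every baseline residual zero. The covariance matrix is then singular and the likelihood has no maximum. An iterated maximum-likelihood fit to one simulated dataset (assumed SDs 250/450/500, correlations 0.3, 0.3 and 0.7, donor effects -50 and -150) shows this over its first three iterations:

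| Quantity | Iteration 1 | 2 | 3 |
|---|---|---|---|
| Baseline slope | 0.909 | 0.991 | 0.9992 |
| Baseline residual variance | 527 | 4.8 | 0.043 |
| Common donor effect | -9.2 | -1.1 | -0.11 |

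The log-likelihood kept rising and the donor effect was driven to zero. Letting the baseline slope differ by visit gives the same collapse.

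**Part 2: baseline as covariate only, one common donor effect.**

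Inputs from section 8.3: 1278 completing eyes at 2:1 is 852 and 426; planning failure rates are 4% and 9%. Eyes without failure: 852 × 0.96 = 818 and 426 × 0.91 = 388, if every 1-year image is gradable.

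Assumed, not in the documents: SD 450 at 1 month and 500 at 1 year; correlation 0.7 between them; correlation 0.3 of each with baseline; true donor effects -60 at 1 month and -100 at 1 year; eyes independent. Corneal diagnosis and the fellow-eye random effect are left out.

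Residual variances and covariance after baseline adjustment:

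- v1 = 450² × (1 - 0.09) = 184275
- v2 = 500² × (1 - 0.09) = 227500
- c = 450 × 500 × (0.7 - 0.09) = 137250

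Weight on 1 month = (v2 - c)/(v1 + v2 - 2c) = 90250/137275 = 0.657.

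Common effect = 0.657 × (-60) + 0.343 × (-100) = -73.7.

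SE of the common effect = √[(v1·v2 - c²)/(v1 + v2 - 2c) × (1/818 + 1/388)] = 25.3.

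SE of the 1-year contrast = √[v2 × (1/818 + 1/388)] = 29.4.

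The bias is 26.3, or 26.3/25.3 = 1.04 SE. The 95% interval of the common effect then covers -100 about 82% of the time. Power is 83% for the common effect (73.7/25.3 = 2.92) and 92.5% for the 1-year contrast (100/29.4 = 3.40).

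Common effect for true effects -60/-100 under other assumptions:

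| SD at 1 month / 1 year | Correlation 0.5 | 0.7 | 0.8 |
|---|---|---|---|
| 400/500 | -72.2 | -67.3 | -61.6 |
| 450/500 | -76.2 | -73.7 | -70.6 |
| 500/500 | -80.0 | -80.0 | -80.0 |
| 500/450 | -83.8 | -86.3 | -89.4 |

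Common effect when the 1-year effect stays at -100 (SD 450/500, correlation 0.7):

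| 1-month effect | 0 | -30 | -60 | -80 | -100 | -120 |
|---|---|---|---|---|---|---|
| Common effect | -34 | -54 | -74 | -87 | -100 | -113 |

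There is no bias when the two effects are equal, and overstatement when the 1-month effect is the larger.

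**The case against.** **Silence is not exclusion.** Section 8.7 does not say that a donor-by-visit term is left out, and it speaks of models and effects in the plural. A reader might infer that the plan has chosen to average the two visits. The text does not support that; it leaves the matter open. This stands, and it makes every figure in Part 2 conditional on the term being omitted.

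**The context points to 1 year.** The endpoint definition, the restriction to eyes with a gradable 1-year image, and the summary tables of baseline, 1-year and change all suggest that a 1-year effect is intended. That is fair as to intent. But the reported effect carries no time point, and an analyst cannot recover the contrast from the named terms.

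**A fuller SAP may settle it.** Section 8.1 calls the analyses a summary, and several sections refer details to the SAP. For this outcome, however, section 8.5 defers only sensitivity analyses, section 8.7 defers nothing, and nothing else in the document respecifies the model.

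**The baseline error would show itself.** A reader might infer that it would silently bias the reported result. It would not: the literal model fails to converge, so it has to be changed before a result exists. What remains is that the change would be made without a pre-specified rule.

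**The sizes are assumed.** This stands. The direction is also unknown, although the background (section 1.1) cites greater long-term cell loss with diabetic donors, which would fit an effect that grows over time.

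**Conclusion.** The point holds in a limited form. The use of baseline is wrong as written and must be corrected before the model can be fitted. The 1-year contrast is not specified, although the endpoint is at 1 year throughout. If the repair keeps a single donor effect, the estimate is a covariance-weighted average that equals the 1-year effect only if the two effects are equal or all the weight falls on 1 year.

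Under the assumptions shown, an effect of -100 at 1 year with -60 at 1 month would be reported as about -74, with a range of -62 to -89 over the SDs and correlations tried. These are illustrations, not estimates for this trial. The documents do not support a claim that the secondary result will be attenuated, or by how much. This is worth fixing for a secondary endpoint; it does not touch the primary analysis of graft failure.

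**What to change.** In section 8.7, or in the SAP, state that:

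- the responses are 1-month and 1-year ECD;
- baseline (eye bank) ECD is a covariate only, with its own slope at each visit;
- the model includes visit, donor diabetes status and donor-by-visit, plus the planned corneal diagnosis and recipient random effect;
- the secondary result is the 1-year donor contrast with its 95% confidence interval and two-sided p-value.

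On the untransformed scale this contrast is the same for 1-year ECD and for change from baseline, because subtracting baseline only shifts its slope by 1. One statement therefore serves both section 8.4.2 and the Protocol Summary. If the fallback to a transformation or ranks is used, state which of the two is analysed. Use the same 1-year contrast in the ECD subgroup and severity models (sections 8.12 and 8.14).

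Another valid repair keeps baseline as a response, drops it as a covariate and includes donor-by-visit. Equal baseline means in the two donor groups should not then be assumed without justification.

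The cost is a few sentences and no new data. The downside is some precision: if the donor effect really is constant over time, the 1-year contrast has the larger SE (29.4 against 25.3 in the illustration, about 16% larger).

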8.8 Safety Analyses

The safety analysis will include events occurring on or after the day of surgery until and including the 12-month visit, or Day 464, whichever occurs first.

All reportable adverse events, operative complications and procedures, post-operative complications and procedures (e.g., dislocation of donor, graft detachment, air injection), and abnormalities noted on ocular exam will be tabulated by donor diabetes status group. These will include but not be limited to:

- Endophthalmitis
- Microbial keratitis
- IOP>25 mmHg
- Corneal Thickness >750 microns
- Definite signs of graft rejection
- Recipient stromal clarity = cloudy

8.9 Protocol Adherence and Retention

The following tabulations and analyses will be performed by donor diabetes status group:

- Protocol and procedural deviations
- Flow chart accounting for all enrolled participants
- Participants who dropped and reasons

8.10 Baseline Descriptive Statistics

Baseline demographic and clinical characteristics will be tabulated overall, and by donor diabetes status group. Additionally, baseline characteristics will be tabulated for cases with graft failure, cases with incomplete follow-up without graft failure, and cases with complete follow-up without graft failure.

Donor characteristics will also be tabulated.

8.11 Planned Interim Analyses

No formal interim efficacy analyses are planned for this study. Compiled safety data reports will be reviewed by the DSMC semi-annually.

8.12 Sub-Group Analyses

Subgroup analyses/assessments of effect modification (interaction) will be conducted separately for the graft failure within the first year after surgery and ECD at one-year. These analyses will be considered exploratory. Additionally, interpretation of the analyses will depend on whether the overall analysis demonstrates a significant treatment group difference; in the absence of such an overall difference, subgroup analyses will be interpreted with caution. The general approach for these exploratory analyses will be to add an interaction term for the subgroup factor, which will be noted in the SAP, by diabetes group into the models used for the primary analyses. For

continuous variables, results will be displayed in subgroups based on cutpoints although the analysis will utilize the variable as continuous. If there is insufficient sample size in a given subgroup, the cutpoints for continuous measures may be adjusted per the observed distribution of values. Cutpoint selection for display purposes will be made masked to the outcome data.

8.13 Multiple Comparison/Multiplicity

There will be no adjustment for primary and secondary analyses.

For comparison of all exploratory analyses, Benjamini-Hochberg false discovery rate adjusted p-values will be calculated within several subcategories.

8.14 Analysis of the Tertiary Exploratory Endpoint

Exploratory analyses will evaluate the effect of donor diabetes status on 1-year graft failure rate with donor diabetes severity defined in the alternative ways as measured by eye bank-determined diabetes risk categorization scores, post-mortem HbA1c, and skin AGEs and oxidation markers. Additionally, the effect of donor diabetes status on 1-year ECD with alternative definitions for donor diabetes severity will be examined. The alternative definitions will be detailed in the SAP.

Potential confounders or interaction terms determined in the analyses of graft failure and ECD will be explored in adjusted models mirroring the primary analyses.

8.15 Additional Tabulations and Analyses

8.15.1 Additional Tabulations

The following tabulations will be performed by donor diabetes status group:

- Additional post-operative study eye procedures
- Immunizations or vaccinations vs signs of graft rejection
- Ocular and systemic diabetic complications

8.15.2 Additional Analyses

The association of donor, recipient, and operative factors potentially related to graft failure within 1-year following DMEK will be evaluated and detailed in the SAP.

Chapter 9: Data Collection and Monitoring

9.1 Case Report Forms and Other Data Collection

Since data are captured retrospectively, direct data entry onto electronic case report forms (CRFs) is not feasible. Thus, paper worksheets will be provided to capture relevant post-operative data for transcription later, which is the preferred method of data capture. When utilized, these will be considered source documentation and must be maintained in the study records. If data is transcribed from the medical record onto electronic forms, the medical record is considered the source document. The source documents must be readily verifiable against the values entered into eCRF, and if paper worksheets are utilized they may be compared to concurrent medical records as well.

9.2 Study Records Retention

Each participating site will maintain appropriate medical and research records for this trial, in compliance with ICH E6 and regulatory and institutional requirements for the protection of confidentiality of participants.

Study documents should be retained for a minimum of 3 years after completion of final grant reporting. These documents should be retained for a longer period, however, if required by local regulations. No records will be destroyed without the written consent of the CWRU CC, if applicable. It is the responsibility of the sponsor to inform the investigator when these documents no longer need to be retained.

9.3 Quality Assurance and Monitoring

Designated personnel from the CWRU CC and the JCHR Data Management and Analysis Center will be responsible for maintaining quality assurance (QA) and quality control (QC) systems to ensure that the clinical portion of the trial is conducted and data are generated, documented and reported in compliance with the protocol, Good Clinical Practice (GCP) and the applicable regulatory requirements, as well as to ensure that the rights and wellbeing of trial participants are protected and that the reported trial data are accurate, complete, and verifiable.

A risk-based monitoring (RBM) plan will be developed and revised as needed during the course of the study, consistent with the FDA “Guidance for Industry Oversight of Clinical Investigations — A Risk-Based Approach to Monitoring” (August 2013).⁵⁶

For the DEKS, data of most importance for monitoring at the site are informed consent, proper characterization of donor and recipient diabetes status, and outcome assessments (graft failure). Therefore, the RBM plan will focus on these areas. All monitoring will be performed remotely. Elements of the RBM plan may include:

- Qualification assessment, training, and certification for sites and site personnel
- Oversight of Institutional Review Board (IRB) coverage and informed consent procedures
- Central (remote) data monitoring: validation of data entry, data edits/audit trail, protocol review of entered data and edits, statistical monitoring, study closeout
- Remotely monitored source data verification, site visit reports

- Tissue accountability
- Communications with site staff
- Patient retention and visit completion
- Quality control reports
- Management of noncompliance
- Documenting monitoring activities
- Adverse event reporting and monitoring

CC representatives or their designees may remotely “visit” the study facilities (eye banks as well as clinical sites) at any time in order to maintain current and personal knowledge of the study through review of records, comparison with source documents, observation and discussion of the conduct and progress of the study. The investigational site will provide access to all source data/documents, and reports for the purpose of monitoring and auditing by the sponsor, and inspection by local and regulatory authorities.

